## **8.2. Adverse Events**

An AE is defined as follows: any untoward medical occurrence in a patient or clinical investigation subject administered a pharmaceutical product that does not necessarily have a causal relationship with this treatment. An AE can, therefore, be any unfavorable and unintended sign (including an abnormal laboratory finding), symptom, or disease temporally associated with the use of a medicinal (investigational) product, whether or not related to the medicinal (investigational) product.

Investigators are responsible for monitoring the safety of patients who have entered this study and for alerting Lilly or its designee to any event that seems unusual, even if this event may be considered an unanticipated benefit to the patient.

The investigator is responsible for the appropriate medical care of patients during the study.

Investigators must document their review of each laboratory safety report.

The investigator remains responsible for following, through an appropriate health care option, AEs that are serious or otherwise medically important, considered related to the investigational product or the study, or that caused the patient to discontinue the investigational product before completing the study. The patient is to be followed until the event resolves, stabilizes with appropriate diagnostic evaluation, or is reasonably explained. The frequency of follow-up evaluations of the AE is left to the discretion of the investigator.

Lack of drug effect is not an AE in clinical studies because the purpose of the clinical study is to establish treatment effect.

After the ICF is signed, study site personnel will record via CRF the occurrence and nature of each patient's preexisting conditions, including clinically significant signs and symptoms of the disease under treatment in the study. In addition, site personnel will record via CRF any change in the condition(s) and any new conditions as AEs. Investigators are to record their assessment of the potential relatedness of each AE to protocol procedure, investigational product, via CRF.

The investigator decides whether he or she interprets each AE as reasonably possibly related to the study product, study procedure, disease under study, or other concomitant medications, or pathologies. To assess the relationship of the AEs, the following is defined:

Reasonably Possibly **Related**: Reasonable possibility that there is a cause and effect relationship between the study product and/or study procedure and the AE.

The investigator answers yes/no when making this assessment.

Planned surgeries and nonsurgical interventions are not to be reported as AEs unless the underlying medical condition has worsened during the course of the study.

If a patient's investigational product is discontinued as a result of an AE, study site personnel must report this to Lilly or its designee via electronic data entry, clarifying if possible, the circumstances leading to any dosage modifications or discontinuations of treatment.

Accurate start and stop dates (and times, where required) are to be reported via electronic data entry for all AEs. Only AEs that are ongoing at the last study visit and/or communication are to be documented as "ongoing."

### **8.2.1. Serious Adverse Events**

An SAE is any AE from this study that results in 1 of the following outcomes:

- death
- initial or prolonged inpatient hospitalization

- a life-threatening experience (that is, immediate risk of dying)
- persistent or significant disability/incapacity
- congenital anomaly/birth defect
- important medical events that may not be immediately life-threatening or result in death or hospitalization but may jeopardize the patient or may require intervention to prevent one of the other outcomes listed in the definition above.

If an SAE occurs after signing the ICF, but prior to receiving investigational product, it needs to be reported ONLY if it is considered reasonably possibly related to study procedure.

Study site personnel must alert Lilly or its designee of any SAE within 24 hours of investigator awareness of the event via a sponsor-approved method. If alerts are issued via telephone, they are to be immediately followed with official notification on study-specific SAE forms. This 24-hour notification requirement refers to the initial SAE information and all follow-up SAE information.

Pregnancy (during maternal or paternal exposure to investigational product) does not meet the definition of an AE. However, to fulfill regulatory requirements any pregnancy (during maternal or paternal exposure to investigational product) must be reported following the SAE process and data are to be collected on the outcome for both mother and fetus.

Investigators are not obligated to actively seek AEs or SAEs in subjects once they have discontinued and/or completed the study (the patient summary CRF has been completed). However, if the investigator learns of any SAE, including a death, at any time after a subject has been discharged from the study, and he/she considers the event reasonably possibly related to the study treatment or study participation, the investigator must promptly notify Lilly.

#### **8.2.1.1. Suspected Unexpected Serious Adverse Reactions**

Lilly has procedures that will be followed for the recording and expedited reporting of suspected unexpected serious adverse events (SUSARs) that are consistent with global regulations and the associated detailed guidances.

#### **8.2.2. Adverse Events of Special Interest**

The following adverse events of special interest (AESIs) will be used to determine the safety and tolerability of ixekizumab over the range of doses selected for this clinical study.

AESIs for ixekizumab are:

- cytopenias (leukopenia, neutropenia, and thrombocytopenia)
- clinically significant hepatic events and/or significant elevations in liver function test changes/enzyme elevations (ALT, AST, bilirubin, and alkaline phosphatase)
- infections
- injection-site reactions
- allergic reactions/hypersensitivities
- cerebrocardiovascular events
- malignancies
- IBD

- depression.

Sites will provide details on some of these AEs as instructed on the CRF. Investigators will also educate patients and/or caregivers about the symptoms of allergic/hypersensitivity reactions and will provide instructions on dealing with these reactions (see also Section 6.6.1). A blood sample will be collected as soon as possible for any patient who experiences an AE of a potential systemic allergic /hypersensitivity reaction during the study as judged by the investigator.

Data on preferred terms associated with cerebrocardiovascular events (defined as death, cardiac ischemic events including MI and hospitalization for unstable angina, hospitalization for heart failure, serious arrhythmia, resuscitated sudden death, cardiogenic shock, coronary revascularization procedure, stroke/transient ischemic attack, peripheral revascularization procedure, peripheral arterial event, and hospitalization for hypertension) will be collected, and these events and any deaths will be adjudicated by an external clinical events committee (CEC) made up of a chairman, 2 cardiologists, and a neurologist.

Data on suspected IBD, as identified by events possibly indicative of ulcerative colitis and Crohn's disease, will be collected and the events will be adjudicated by an external CEC with expertise in IBD.

The role of external CECs is to adjudicate defined clinical events in a blinded, consistent, and unbiased manner throughout the course of a study. The purpose of the CEC for adjudication of cerebrocardiovascular events and the CEC for adjudication of suspected IBD events is to ensure that all reported events are evaluated uniformly by a single group.

### **8.2.3. Complaint Handling**

Lilly collects product complaints on investigational products and drug delivery systems used in clinical studies in order to ensure the safety of study participants, monitor quality, and to facilitate process and product improvements.

Patients will be instructed to contact the investigator as soon as possible if he or she has a complaint or problem with the investigational product so that the situation can be assessed.

## **8.3. Treatment of Overdose**

Refer to the IB.

## **8.4. Safety Assessments**

### **8.4.1. Electrocardiograms**

For each patient, 12-lead ECGs must be collected locally at screening ([Appendix 2](#)). Patients are to be resting for 5 minutes prior to the ECG. It is recommended that patients be in a supine position.

Any clinically significant findings from ECGs that result in a diagnosis and that occur after the patient receives the first dose of the investigational treatment are to be reported to Lilly or its

designee as an AE via CRF. Any clinically significant ECG findings prior to receiving drug are to be reported as a preexisting condition.

#### **8.4.2. Vital Signs**

For each patient, vital signs measurements are to be conducted according to the Schedule of Activities ([Appendix 2](#)). Vital signs include BP, pulse, and temperature. Patients are to be resting for a minimum of 5 minutes prior to vital sign collection.

Any clinically significant findings from vital signs measurement that result in a diagnosis and that occur after the patient receives the first dose of study treatment are to be reported to Lilly or its designee as an AE via CRF.

#### **8.4.3. Laboratory Tests**

For each patient, laboratory tests detailed in ([Appendix 3](#)) will be sent to central laboratory for processing and are to be conducted according to the Schedule of Activities ([Appendix 2](#)). Please reference the central laboratory manual for specific instructions.

Urine pregnancy test and PPD/T-SPOT® will be collected and read/analyzed locally.

QuantiFERON®-TB Gold test will be collected and read/analyzed either centrally or locally.

If required per local regulations, urine testing for pregnancy may occur at intervals as required during the study treatment period and/or follow-up period.

Any clinically significant findings from laboratory tests that result in a diagnosis and that occur after the patient receives the first dose of investigational product are to be reported to Lilly or its designee as an AE via CRF.

#### **8.4.4. Physical Examination**

For each patient, a complete physical examination must be conducted according to the Schedule of Activities ([Appendix 2](#)).

Any clinically significant finding from a complete physical examination that results in a diagnosis and that occurs after the patient receives the first dose of study treatment is to be reported to Lilly or its designee as an AE via CRF.

#### **8.4.5. Eye Symptom Assessment**

At each study visit, study healthcare providers will evaluate the patient for any symptoms of anterior uveitis as specified in the Schedule of Activities ([Appendix 2](#)). If the patient has no prior ophthalmologist diagnosed anterior uveitis and develops eye pain or discomfort, eye redness, blurring of vision, or any other symptoms suggestive of anterior uveitis, the patient must be evaluated by an ophthalmologist. If a patient has prior history of ophthalmologist diagnosed anterior uveitis, then she/he must be evaluated by a physician for recurrence of anterior uveitis (whenever possible, diagnosis is to be confirmed by an ophthalmologist).

#### 8.4.6. Chest X-Ray and Tuberculosis Testing

For each patient, a posterior anterior chest x-ray and TB testing must be conducted according to the Schedule of Activities ([Appendix 2](#)).

The posterior anterior chest x-ray or results will be reviewed by the investigator or designee prior to baseline randomization to exclude patients with active TB infection.

Any clinically significant findings from a posterior anterior chest x-ray or TB testing that result in a new diagnosis and that occur after the patient receives the first dose of study treatment is to be reported to Lilly or its designee as an AE via CRF.

**Patients with no TB test (Purified Protein Derivative [PPD] and/or Interferon-Gamma Release Assay) results on file:** These patients will be tested at screening as indicated on the Schedule of Activities ([Appendix 2](#)) for evidence of active or latent TB indicated by a positive PPD skin test response, defined as  $\geq 5$  mm diameter of induration, between approximately 2 and 3 days after test application, regardless of BCG vaccination history. In countries where the Interferon-Gamma Release Assay (QuantiFERON®-TB Gold test, or T-SPOT®) is available and, in the judgment of the investigator, preferred as an alternative to the PPD skin test for the evaluation of TB infection, it may be used instead of the PPD test (positive tests excluded). The QuantiFERON-TB Gold test may be read locally or centrally, while the T-SPOT must be read locally. If the QuantiFERON-TB Gold test is indeterminate or the T-SPOT is invalid or borderline, 1 retest is allowed. If the retest for the QuantiFERON-TB Gold test is indeterminate or the retest for the T-SPOT is invalid or borderline, then the patient is excluded from enrolling in the study.

However, patients with a PPD skin test  $\geq 5$  mm induration or a positive QuantiFERON-TB Gold or positive T-SPOT test at screening but no other evidence of active TB may be rescreened 1 time and may be enrolled without repeating a PPD or QuantiFERON-TB Gold test or T-SPOT (TB test) if the following conditions are met:

- after receiving at least 4 weeks of appropriate latent TB infection (LTBI) therapy.
- with no evidence of hepatotoxicity (ALT/AST must remain  $\leq 2 \times \text{ULN}$ ) upon retesting of serum ALT/AST prior to randomization. Such patients must complete appropriate latent TB infection (LTBI) therapy during the course of the study in order to remain eligible.
- meet all other inclusion/exclusion criteria for participation.

If rescreening occurs within 6 months of the initial screening posterior anterior chest x-ray, there is no necessity for repeat of the chest x-ray for considering enrollment.

**Patients with negative TB test results on file:** Patients with documentation of a negative test result within 3 months prior to baseline (Week 0; Visit 2) do not need a TB screen at Visit 1. Documentation of a PPD test result must include a record of the size of the induration response documenting either no induration or induration measuring  $< 5$  mm in diameter. A PPD test recorded as negative without documenting the size of induration will result in a required test at screening to determine patient eligibility.

**Patients with positive TB test results on file:** Patients with prior history of a positive TB test are not to have a TB test at Visit 1. Documentation of this history and of at least 4 weeks of appropriate latent TB treatment prior to baseline (Week 0, Visit 2) and continued treatment during the study is required to attain and maintain study eligibility. Patients who have a documented history of completing an appropriate TB treatment regimen with no history of re-exposure to TB since their treatment was completed and no evidence of active TB are eligible to participate in the study. Patients who have had household contact with a person with active TB are excluded, unless appropriate and documented prophylaxis for TB was completed.

#### **8.4.7. Quick Inventory of Depressive Symptomatology–Self-Report (16 Items)**

For each patient, a QIDS-SR16 assessment will be collected according to the Schedule of Activities ([Appendix 2](#)).

Any clinically significant findings from the QIDS-SR16 assessment that result in a diagnosis and that occur after the patient receives the first dose of study treatment are to be reported to Lilly or its designee as an AE via CRF.

The QIDS-SR16 is a self-administered 16-item instrument intended to assess the existence and severity of symptoms of depression as listed in the American Psychiatric Association's Diagnostic and Statistical Manual of Mental Disorders, 4th Edition (APA 1994). A patient is asked to consider each statement as it relates to the way they have felt for the past 7 days. There is a 4-point scale for each item ranging from 0 to 3. The 16 items corresponding to 9 depression domains that are summed to give a single score ranging from 0 to 27, with higher scores denoting greater symptom severity. The domains assessed by the instrument are (1) sad mood, (2) concentration, (3) self-criticism, (4) suicidal ideation, (5) interest, (6) energy/fatigue, (7) sleep disturbance (initial, middle, and late insomnia or hypersomnia), (8) decrease/increase in appetite/weight, and (9) psychomotor agitation/retardation. Additional information and the QIDS-SR16 questions may be found at the University of Pittsburgh IDS/QIDS internet page (IDS/QIDS home page [WWW]).

#### **8.4.8. Columbia Suicide Severity Rating Scale**

The C-SSRS (Posner et al. 2007, C-SSRS web site [WWW]) is a scale that captures the occurrence, severity, and frequency of suicide-related ideations and behaviors during the assessment period. The C-SSRS must be administered by appropriately trained site personnel. The tool was developed by the National Institute of Mental Health (NIMH) Treatment of Adolescent Suicide Attempters (TASA) trial group for the purpose of being a counterpart to the Columbia Classification Algorithm of Suicide Assessment (C-CASA) categorization of suicidal events. Patients will be assessed according to the Schedule of Activities ([Appendix 2](#)).

The Self-Harm Supplement Form is a 1 question eCRF questionnaire that is completed at any visit, including baseline visits, asking for the number of suicidal or nonsuicidal self-injurious behaviors the patient experienced since last assessment. For each unique event identified, a

questionnaire (Self-Harm Follow-Up Form) which collects supplemental information on the self-injurious behavior must be completed. This information is then documented in the eCRF.

#### **8.4.9. Immunogenicity**

For each patient, an immunogenicity sample will be collected according to the Schedule of Activities ([Appendix 2](#)).

Additionally, a blood sample will be collected, as soon as possible, for any patient who experiences a potential systemic allergic/hypersensitivity reaction during the study as judged by the investigator. These samples will be tested for immunogenicity and PK, while other laboratory tests may be performed as needed to elucidate the cause of the allergic/hypersensitivity reaction.

#### **8.4.10. Safety Monitoring**

Lilly will periodically review evolving aggregate safety data within the study by appropriate methods.

If a study patient experiences elevated ALT  $\geq 3$ xULN, alkaline phosphatase  $\geq 2$ xULN, or elevated total bilirubin  $\geq 2$ xULN, clinical and laboratory monitoring is to be initiated by the investigator. Details for hepatic monitoring depend upon the severity and persistence of observed laboratory test abnormalities. For other AESIs or abnormal lab results, please refer to the appropriate protocol section that addresses these topics. To ensure patient safety and comply with regulatory guidance, the investigator is to consult with the Lilly clinical research physician/clinical research scientist regarding collection of specific recommended clinical information and follow-up laboratory tests. See [Appendix 4](#).

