### 7.1. Discontinuation from Study Treatment

#### 7.1.1. *Permanent Discontinuation from Study Treatment*

The following criteria must be followed for discontinuation from study treatment.

- [1] Discontinuation of the investigational product for abnormal liver tests should be considered by the investigator when a patient meets 1 of the following conditions after consultation with the Lilly designated medical monitor:
  - ALT or AST >8 times ULN
  - ALT or AST >5 times ULN for more than 2 weeks
  - ALT or AST >3X ULN and total bilirubin level >2 times ULN or prothrombin time >1.5 times ULN
  - ALT or AST >3 times ULN with the appearance of fatigue, nausea, vomiting, right upper-quadrant pain or tenderness, fever, rash, and/or eosinophilia (>5%)
  - alkaline phosphatase >2.5 times ULN and total bilirubin >2 times ULN
  - alkaline phosphatase >2.5 times ULN with the appearance of fatigue, nausea, vomiting, right upper quadrant pain or tenderness, fever, rash, and/or eosinophilia (>5%)
- [2] Other laboratory tests (**Note:** Laboratory test(s) that may result in discontinuation based on a single result may be repeated only once if there is a technical error or clinical reason to believe a result may need to be retested. Laboratory tests can only be repeated after consultation with Lilly medical. Investigational product should not be administered in these cases until retest result is available.):

- Neutrophil (segmented) counts (see safety monitoring for neutropenia in Section 8.4.10.1):
    - $<500$  cells/ $\mu\text{L}$  ( $<0.50 \times 10^3/\mu\text{L}$  or  $<0.50$  GI/L)
    - $\geq 500$  and  $<1000$  cells/ $\mu\text{L}$  ( $\geq 0.50 \times 10^3/\mu\text{L}$  and  $<1.00 \times 10^3/\mu\text{L}$  or  $\geq 0.50$  GI/L and  $<1.00$  GI/L) (based on 2 test results; the second test performed within 1 week from knowledge of the initial result)
    - $\geq 1000$  and  $<1500$  cells/ $\mu\text{L}$  ( $\geq 1.00 \times 10^3/\mu\text{L}$  and  $<1.50 \times 10^3/\mu\text{L}$  or  $\geq 1.00$  GI/L and  $<1.50$  GI/L) (based on 3 test results as specified in Section 8.4.10.1)
      - AND - a concurrent infection
  - Total WBC count  $<2000$  cells/ $\mu\text{L}$  ( $<2.00 \times 10^3/\mu\text{L}$  or  $<2.00$  GI/L)
  - Lymphocyte count  $<500$  cells/ $\mu\text{L}$  ( $<0.50 \times 10^3/\mu\text{L}$  or  $<0.50$  GI/L)
  - Platelet count  $<50,000$  cells/ $\mu\text{L}$  ( $<50 \times 10^3/\mu\text{L}$  or  $<50$  GI/L)

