## Appendix 4. Hepatic Monitoring Tests for Treatment-Emergent Abnormality

---

Selected tests may be obtained in the event of a treatment-emergent hepatic abnormality and may be required in follow-up with patients in consultation with the Lilly, or its designee, clinical research physician.

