	
Elevations in hepatic laboratory tests (ALT, AST, ALP, total bilirubin) using Performing Lab Reference Ranges are defined as:
 
 
• Include scheduled visits, unscheduled visits, and repeat measurements.
 
• Alanine aminotransferase (ALT) or aspartate aminotransferase (AST): maximum postbaseline measurement <math>\geq 3</math> times (<math>3\times</math>), 5 times (<math>5\times</math>), 10 times (<math>10\times</math>), and 20 times (<math>20\times</math>) the Performing Lab upper limit of normal (ULN) for all patients with a postbaseline value. 
 
○ The analysis of <math>3\times</math> ULN will contain 4 subsets: patients whose non-missing maximum baseline value is <math>\leq 1\times</math> ULN, <math>>1\times</math> ULN to <math><3\times</math> ULN, <math>\geq 3\times</math> ULN, or missing.
 
○ The analysis of <math>5\times</math> ULN will contain 5 subsets: patients whose non-missing maximum baseline value is <math>\leq 1\times</math> ULN, <math>>1\times</math> ULN to <math><3\times</math> ULN, <math>\geq 3\times</math> ULN to <math><5\times</math> ULN, <math>\geq 5\times</math> ULN, or missing.
 
○ The analysis of <math>10\times</math> ULN will contain 6 subsets: patients whose non-missing maximum baseline value is <math>\leq 1\times</math> ULN, <math>>1\times</math> ULN to <math><3\times</math> ULN, <math>\geq 3\times</math> ULN to <math><5\times</math> ULN, <math>\geq 5\times</math> ULN to <math><10\times</math> ULN, <math>\geq 10\times</math> ULN, or missing.
 
○ The analysis of <math>20\times</math> ULN will contain 7 subsets: patients whose non-missing maximum baseline value is <math>\leq 1\times</math> ULN, <math>>1\times</math> ULN to <math><3\times</math> ULN, <math>\geq 3\times</math> ULN to <math><5\times</math> ULN, <math>\geq 5\times</math> ULN to <math><10\times</math> ULN, <math>\geq 10\times</math> ULN to <math><20\times</math> ULN, <math>\geq 20\times</math> ULN, or missing.
 
 
 
	
Fisher’s exact test for Safety Population and summary for IR Population: Elevations in hepatic laboratory tests: maximum baseline category to abnormal maximum postbaseline category

Special Safety Topic	Definition / Derivation	Analysis / Summary / Listing

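### The hepatic-monitoring trigger in Protocol 8.4.10 omits AST, although every aminotransferase condition for considering discontinuation in 7.1.1 counts an AST rise

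*Protocol*

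**What the plan says.** **Trigger.** Protocol 8.4.10 (Safety Monitoring) sets three thresholds: ALT at least 3 times ULN, alkaline phosphatase at least 2 times ULN, total bilirubin at least 2 times ULN. If any is met, "clinical and laboratory monitoring is to be initiated by the investigator". The details depend on how severe and persistent the abnormality is. The paragraph refers other special-interest events and abnormal results to their own sections. It then says that the investigator "is to consult with the Lilly clinical research physician/clinical research scientist regarding collection of specific recommended clinical information and follow-up laboratory tests".

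**Conditions for considering discontinuation.** Protocol 7.1.1, criterion [1], lists six hepatic conditions. Two concern alkaline phosphatase. The other four concern aminotransferases, and each names AST beside ALT. Two of them matter most here: "ALT or AST >5 times ULN for more than 2 weeks" and "ALT or AST >3X ULN and total bilirubin level >2 times ULN or prothrombin time >1.5 times ULN". These are not automatic stops. The investigator should consider discontinuation "after consultation with the Lilly designated medical monitor".

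**Elsewhere.** AST is paired with ALT in exclusion criterion [48], in the latent-tuberculosis rescreening rule (8.4.6) and in the hepatic events of special interest (8.2.2). SAP Table RHBX.6.8 tabulates "Alanine aminotransferase (ALT) or aspartate aminotransferase (AST): maximum postbaseline measurement" from 3 times ULN upward. Appendix 4 offers hepatic tests that "may be obtained in the event of a treatment-emergent hepatic abnormality and may be required in follow-up with patients", in consultation with the sponsor's physician.

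**The concern.** The trigger should catch a liver signal before, or at the latest when, a discontinuation condition comes into play. For ALT it does: any ALT above 3 times ULN has already passed the trigger. For AST it does not. A patient whose only abnormal liver test is AST can reach a level at which discontinuation should be considered without meeting any of the three thresholds that start required monitoring.

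At stake is timely follow-up in a narrow group. The first AST value is seen, because Protocol 8.2 requires documented review of every laboratory safety report. What no rule clearly requires is the next test, and two of the four conditions cannot be judged without one.

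**Working it through.** The plan gives no figure on this point to reproduce. The check sets the rules side by side and then reads the visit schedule.

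**Step 1. Trigger against conditions.** Take a patient with raised AST, ALT below 3 times, alkaline phosphatase below 2 times and bilirubin below 2 times ULN. The 8.4.10 triggers met are 0 of 3. Against 7.1.1 [1]:

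| Aminotransferase condition | Can isolated AST meet it? | What is needed to know |
|---|---|---|
| Above 8 times ULN | Yes | One AST value |
| Above 5 times ULN for over 2 weeks | Yes | A second AST more than 14 days later |
| Above 3 times ULN, with bilirubin above 2 times or prothrombin time above 1.5 times ULN | Only through prothrombin time; such a bilirubin would itself be a trigger | A prothrombin time |
| Above 3 times ULN with listed symptoms or eosinophilia | Yes | One AST value and the presentation; hematology is scheduled at the same post-baseline visits |

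Rows 1 and 4 need no follow-up test, and they lead to sponsor consultation under 7.1.1 itself. The practical gap is row 2 and the prothrombin-time part of row 3.

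**Step 2. Is AST covered elsewhere?**

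- 8.2 counts an abnormal laboratory finding as a possible adverse event. It requires medically important events to be followed to resolution or explanation, but leaves the frequency to the investigator.
- The consultation sentence in 8.4.10 is not limited to ALT, but it states no AST level.
- Appendix 4 is permissive and states no level.
- Deviation [D1] in SAP Table RHBX.6.12 (sponsor not consulted) applies only once a discontinuation condition has been met.

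Each helps. None sets an AST threshold that starts monitoring.

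**Step 3. What the schedule shows, and what it does not.** Inputs are the study days and windows in Protocol Appendix 2. Nominal gap = later day − earlier day. Range = nominal gap ± (sum of the two windows).

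- Weeks 4 to 8: 56 − 28 = 28 days; ± (2 + 4) gives 22 to 34.
- Each gap from Week 8 to Week 36: 28 days; ± (4 + 4) gives 20 to 36.
- Weeks 36 to 44: 308 − 252 = 56 days; ± (4 + 7) gives 45 to 67.
- Weeks 44 to 52: 364 − 308 = 56 days; ± (7 + 7) gives 42 to 70.

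The shortest gap, 20 days, already exceeds 14. A persistent rise would therefore show at the next scheduled chemistry, nominally 28 − 14 = 14 or 56 − 14 = 42 days after the two-week mark.

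Post-baseline chemistry through Week 52 falls at Weeks 4, 8, 12, 16, 20, 24, 28, 32, 36, 44 and 52, which is 11 visits. Prothrombin time is scheduled at 4 of them (Weeks 16, 24, 36, 52), leaving 11 − 4 = 7 without it.

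These figures hold equally for ALT. 8.4.10 fixes no repeat interval and requires no prothrombin time for either enzyme. They describe the schedule and do not measure the effect of leaving AST out.

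**The case against.** The strongest case is that this is a wording point. AST elevation is a hepatic event of special interest. 8.4.10 sends such events to their own sections, 7.1.1 names AST and calls for consultation, and 8.2 imposes a follow-up duty without any threshold. Read together, these can be taken to cover a marked AST rise. An ALT-based trigger may also be deliberate: the SAP's combined criterion with bilirubin and its hepatotoxicity plot use ALT alone, and AST can come from muscle. Finally, adding AST to the trigger would give it only the open-ended monitoring that ALT has now.

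Much of this stands. A reader might infer that an isolated AST rise goes without follow-up, or that all four conditions could be met unnoticed. The documents do not support either reading: the first value is reviewed, general follow-up applies, and two conditions can be recognised without a further test. A reader might also take the 28- and 56-day gaps, or the 7 visits without prothrombin time, as the size of the AST problem. They are not, because ALT faces the same schedule.

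What does not stand is that the gap is closed. None of the covering texts gives an AST level, and the ALT-only items in the SAP are reporting rules that do not govern patient care.

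**Conclusion.** The inconsistency is certain on the text: AST appears in 4 of 4 aminotransferase conditions and in 0 of 3 monitoring triggers. Its consequence is modest. It concerns patients with AST at least 3 times ULN, ALT below 3 times, and alkaline phosphatase and bilirubin both below 2 times ULN. It bears on the two-week persistence condition and the prothrombin-time part of the above-3-times condition. The likely harm is delayed recognition in a few patients; the number is not given and is probably small.

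This assumes that no document outside the protocol and SAP sets an AST rule. The central laboratory manual (cited in Protocol 8.4.3) and the German-site liver rule (mentioned in SAP Table RHBX.6.12) were not available. If either covers AST, the change only aligns the wording. Power, type I error and the efficacy analyses are unaffected. The change is worth making because it is nearly free.

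**What to change.** In Protocol 8.4.10, change the first trigger from ALT to ALT or AST at 3 times ULN or more. The SAP already uses that level for AST; the sponsor's clinicians should confirm it. AST then gets the same monitoring as ALT.

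That edit does not settle timing. To close the timing gap for both enzymes, add a separate instruction: repeat the test just after day 14 when ALT or AST exceeds 5 times ULN, and add a prothrombin time when either exceeds 3 times ULN. The neutrophil rule in 7.1.1 [2], which fixes a second test within 1 week, is a model.

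The cost is two words for the trigger, a sentence for the timing, and a few extra tests. Appendix 3 already permits unscheduled chemistry panels, and Appendix 4 already lists prothrombin time. Some repeats will be for AST of muscle origin, which creatine phosphokinase on the existing chemistry panel can help identify.
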